Visit (V) Phone contact (P)	V 1	V 2	P 3	P 4	V 5	P 6	V 7	V 8	P 9	P 10	V 11	P 12	V 13	V 14	P 15
Time of visit	-2	0	1 day after V2	1 week after V2	2 weeks after V2	4 weeks after V2	6 weeks after V2	7 weeks after V2	1 day after V8	1 week after V8	2 weeks after V8	4 weeks after V8	6 weeks after V8	7 weeks after V8	30 days after V14
Visit window (days)¹		+3			±1	±1	+3	±3			±1	±1	+3	±3	+7
Chemistry, Hematology	X												X		
1,5-anhydroglucitol		X					X						X		
Fructosamine		X					X						X		
Urine Pregnancy testing ³	X													X	
Infusion site exam		X			X		X	X			X		X	X	
Pairing of Subjects Pump and Subject Number in Carelink	X														
Instruct in use of BG meter	X														
Hand out and instruct in use of diary	X	X	X	X	X	X	X		X	X	X	X	X		
Training in diabetes and carbohydrate counting ⁴	X	X													
Training in pump use ⁴	X	X													
Remind Subjects to bring BG meter to site visit	X			X		X	X			X		X	X		
Upload pump/ BG meter data into Carelink		X	X	X	X	X	X	X	X	X	X	X	X	X	
Dose adjustments/Pump Setting Review	X	X	X	X	X	X	X	X	X	X	X	X	X	X	
Instruct in use of trial product ⁵		X	X	X	X	X	X	X	X	X	X	X	X		
Drug Accountability ⁵		X					X	X					X	X	
Drug Dispensing ⁵		X						X							
End of treatment														X	
Attend visit fasting ⁶							X						X		
Remind subject to change sensor prior to meal test visit						X						X			

¹ Visit windows are relative to randomization (Visit 2) and Treatment Period 2 Start (Visit 8) and End of Treatment

² Meal tests should not be performed on days of the CGM sensor insertion or on Day 7 of the current sensor session. Meal test will consist of blood draws at the following time points: -2 min, 0 min, 30 min, 60 min, 120 min, and 180 min

³ Urine pregnancy testing to be performed on women of child bearing potential only

⁴ To be performed by qualified site staff

⁵ At Visit 2 (Randomization) study medication will be dispensed. At visit 8 (Treatment period 2) study medication will be dispensed.

⁶ Fasting is considered 8 hours with no food or drink, other than water

3 Rationale

The Medtronic 670G HCL system offers closer to physiologic algorithm based insulin delivery with variable basal insulin administration which interacts with CGM derived, glucose levels.

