To compare Fiasp[®] in terms of glycemic control with a focus on post-prandial 1-hour plasma glucose level and system-based outcomes to NovoLog[®] insulin when used in the Medtronic mini Med 670G HCL system (operating in auto-mode) in patients with type 1 diabetes.

Secondary objectives

- Assessment of post-prandial glucose regulation (Continuous glucose monitor data, and 1,5 anhydroglucitol levels)
- Evaluation of cumulative glycemic control (HbA1c)
- Measurement of HCL parameters
- Reporting of Fructosamine levels

Endpoints

Primary Endpoint

- Post-prandial 1-hour plasma glucose levels at 6 weeks into start of therapy in each arm

Secondary Endpoints

- Post- prandial 2- hour plasma glucose levels at 6 weeks into start of therapy in each arm
- HbA1c and 1, 5 AG levels prior to cross-over, and at end of study
- Glycemic excursion parameters: Time spent within glycemic ranges as below will be reported and analyzed. Time spent in specific ranges will be expressed as a percentage of total time on treatment.
 - o Time spent (%) within 70-180 mg/dl
 - o Time spent (%) < 70 mg/dl
 - o Time spent (%) >200 mg/dl
 - o Hypoglycemia (differentiated as level 1 or level 2) (Reference 11)
 - o Severe hypoglycemia
- Insulin related parameters

- Total daily dose
- change in %bolus and %basal from baseline
- Auto basal / basal amount (per day)
- Change in insulin : carbohydrate ratio from baseline
- Active insulin time
- Pump related parameters
 - Time spent (%) in auto mode
 - Time spent (%) in manual mode
 - Auto mode exits (with reasons for exit)
 - Infusion site reactions reported by patient
 - Occlusion events reported by patient

This is an exploratory, single-center, randomized, open label, active-controlled, complete cross-over trial comparing safety and efficacy of Fiasp[®] versus NovoLog[®] when used in the Medtronic MiniMed 670G system in subjects with T1DM.

Study timeline:

FPV expected to be April 2019 with LPV in January 2020. The total duration of the trial participation for subjects is approximately 20 weeks as shown below:

Visit 1: Screening

Visit 2: Randomization /Treatment Period 1 Start / Day 0

Visit 3: Phone visit / 1 day after randomization

Visit 4: Phone visit / 1 week after randomization

Visit 5: Office visit / Week 2

Visit 6: Phone visit / Week 4

Visit 7: Office visit / Week 6 / Meal test

Visit 8: Office visit / Week 7/ Treatment Period 2 Start

Visit 9: Phone follow-up / 1 day after Visit 8

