6.3.2.3 Change of infusion set and reservoir

Infusion sets will not be provided by the study. The subjects should be able to continue to afford and use their own personal infusion sets throughout the entire study period. The type of infusion set should be recorded in the source documentation at screening and the subjects should remain on the same type of sets throughout the duration of the entire study period.

The Subjects should be instructed to routinely change infusion set in intervals not exceeding 3 days (2 days for SureT[®] (Easy-set[®])). Infusion set and reservoir should be changed at the same time. The trial products should preferably be administered in the abdominal wall. The Investigator should ensure that the Subject is instructed in the following:

- The infusion region chosen should remain unchanged throughout the trial
- The infusion site should be rotated within the same region
- The infusion set should preferably be inserted in the same way

The Subject should change infusion set and reservoir at the site under supervision by the Investigator at randomization (Visit 2) and at end of treatment (Visit 14) due to the change from pre-trial insulin to trial product. The Investigator should evaluate the skin for any local skin irritation or skin infection at every office visit. Any abnormal clinically significant findings should be recorded as an infusion site reaction, as detailed in Section [7](#).

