6.3.5 Site insertion examination

The site insertion examination will be performed as outlined in the flow chart (section [2](#)). Site insertion examination will include a skin examination of the subjects preferred infusion set site insertion.

Any abnormal and/or clinically significant findings must be recorded in the Subject's medical record or reviewed for an adverse event.

Any clinically significant worsening from screening, as well as any new abnormal and clinically significant findings, must be reported as an AE in accordance with section 9.

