9.1.8 Infusion site reactions

If suspicion of an infusion site reaction occurs, the Subject should be instructed to call the site staff as soon as possible for further guidance.

Infusion site reactions at the site of trial product(s) administration must be recorded as an AE throughout the trial from start of screening (Visit 1) until the end of treatment visit (Visit 14).

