12.4 Secondary endpoints

- Difference in HbA1c between periods will be assessed.
 - Glycemic excursion parameters. Time spent within glycemic ranges as below will be reported and analyzed. Time spent in specific ranges will be expressed as a percentage of total time on treatment.
 - o Time spent (%) within 70-180 mg/dl
 - o Time spent (%) < 70 mg/dl
 - o Time spent (%) >200 mg/dl
 - o Hypoglycemia
 - o Severe hypoglycemia

The time spent within 70-180 mg/dL, <70 mg/dL, and >200 mg/dL, and hypoglycemia is defined for each subject as the accumulated time in hours spent within the above intervals as recorded by the continuous glucose monitoring component of the MiniMed 670G system. Comparison between the NovoLog® and Fiasp® groups will be analyzed by using linear mixed modeling for repeated measurements for each range. The models will include treatment and period as factors, and subject as a random effect.

- Insulin related parameters
 - o Total daily dose
 - o change in %bolus and %basal from baseline
 - o Auto basal / basal amount (per day)
 - o Change in insulin : carbohydrate ratio from baseline
 - o Active insulin time

- Pump related parameters
 - o Time spent (%) in auto mode
 - o Time spent (%) in manual mode
 - o Auto mode exits (with reasons for exit)
 - o Infusion site reactions reported by patient
 - o Occlusion events reported by patient

Secondary endpoints will be assessed through duration of follow-up in the study.

13 Ethics

The trial will be conducted in compliance with ICH GCP and applicable regulatory requirements, and in accordance with the Declaration of Helsinki.

All Subjects included in the trial will be randomized to either Fiasp[®] or NovoLog[®].

The most common side effect of all available insulin preparations is hypoglycemia. The Investigator will explain to the Subject how they should check their BG meter and what precautions to take.

Subjects randomized in the trial will be transferred to a treatment regimen anticipated to be either better than or equal to the treatment they receive at the time they entered the trial.

At the end of treatment, the Subject and Investigator will decide on the best available treatment on the market.

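### The infusion-site reaction endpoint is worded as patient-reported only, narrower than the protocol's own recording rules, so reactions found at the scheduled skin exam are collected but enter no planned comparison

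*Combined protocol and SAP*

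**What the plan says.** **Endpoint.** The endpoint list in Section 4 and the list in Section 12.4 use the same words: "Infusion site reactions reported by patient". The item stands under pump-related parameters, beside patient-reported occlusion events.

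**Collection.** Section 6.3.2.3 states: "The Investigator should evaluate the skin for any local skin irritation or skin infection at every office visit". It continues: "Any abnormal clinically significant findings should be recorded as an infusion site reaction". Section 6.3.5 describes the procedure ("Site insertion examination will include a skin examination of the subjects preferred infusion set site insertion") and requires that clinically significant worsening from screening, and "any new abnormal and clinically significant findings, must be reported as an AE in accordance with section 9". Section 9.1.8 adds: "Infusion site reactions at the site of trial product(s) administration must be recorded as an AE throughout the trial", from Visit 1 to Visit 14.

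**Schedule.** The flow chart in Section 2 has a row "Infusion site exam", marked at V2, V5, V7, V8, V11, V13 and V14. A separate row for infusion site reactions is marked at every contact from V2 to V14, phone contacts included.

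**Analysis.** Section 12.1 says that efficacy and safety endpoints are summarized and analyzed on the full analysis set. Section 12.4 gives a mixed model for the glycemic ranges and no method for infusion site reactions. Section 12 lists no AE endpoint and no AE table by treatment.

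**Design.** Section 4 calls the study an "exploratory, single-center, randomized, open label, active-controlled, complete cross-over trial".

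**The concern.** The endpoint restricts infusion site reactions by who reported them; the recording rules do not. A reaction that the subject did not mention, but that staff saw at a scheduled exam, is an infusion site reaction under Section 6.3.2.3 and an AE under Section 9.1.8, yet it does not fit the endpoint's label. The trial compares two insulins delivered through an infusion set, so local tolerability is a natural safety question, and this is the only endpoint on such reactions.

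Subjects know which insulin they are using, and mentioning a mild reaction may depend on what they expect of it. The diary in Section 6.5.1 lists only hypoglycemic and unexplained hyperglycemic episodes, so patient report relies on questions at each contact (Section 9.2) and on calls to the site (Section 9.1.8). A second source, scheduled alike in both periods, would help, but the named endpoint does not use it.

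**Working it through.** The plan gives no figure to reproduce here: it states no expected reaction rate, and the sample size in Section 12.2 does not concern this endpoint. The check sets the texts side by side.

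1. **Is the restriction deliberate or a slip?** It appears in the same words in Sections 4 and 12.4, so it reads as a stated definition.

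2. **How often is the skin examined?** There are eight office visits (V1, V2, V5, V7, V8, V11, V13, V14). The flow chart marks the exam at seven; the exception, V1, precedes any trial product. After randomization there are six exams: V5, V7 and V8 in Period 1, and V11, V13 and V14 in Period 2, so three per insulin. The flow chart does not give the order of procedures at V8; counting that exam to Period 1 assumes it is done before the switch.
   - All 40 randomized subjects complete: 6 × 40 = 240 exams.
   - The 36 subjects left after the plan's 10% dropout: 6 × 36 = 216 exams.

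   These are counts of exams, not of missed reactions.

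3. **Are exam findings recorded?** Yes, where clinically significant: as infusion site reactions (6.3.2.3), as AEs if new or worsened (6.3.5), and as AEs with no limit on who detects them (9.1.8). The reference in 6.3.2.3 to further detail points to Section 7, which is Trial supplies; the matching text is in 9.1.8.

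4. **Are they analyzed?** No planned analysis names them. The only listed endpoint on these reactions is the patient-reported one, and Section 12 has no AE comparison. The design rationale in Section 4 gives the safety sources as hypoglycemia records, patient logs and closed-loop system parameters; it names neither AEs nor skin exams.

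5. **What does the endpoint count?** On the literal reading, exam-detected reactions are excluded. On a looser reading, Section 6.3.2.3 makes them infusion site reactions and they count, but then the endpoint's label is wrong. The documents do not settle it, so two analysts could count different events from the same data.

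6. **How much could the exam add?** Sets are changed at intervals of no more than 3 days, with rotation within the region (6.3.2.3). A 7-week period has 49 days, and 49 / 3 = 16.3, so about 16 or more sites per period against three exams. Patient report must remain the main source, and the exam is a supplement of unknown yield.

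**The case against.** The strongest reply is that nothing is lost. Sections 6.3.2.3, 6.3.5 and 9.1.8 together ensure that new or worsened clinically significant findings are recorded and can be placed in a treatment period. A patient-reported measure with AE recording beside it is a legitimate choice. The item is one line among pump parameters in an exploratory trial, with no model attached. Subjects are asked about AEs at every contact, so the two sources probably overlap heavily.

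Most of this stands, and it rules out several stronger readings:

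- A reader might infer that exam findings go unrecorded, or that Section 6.3.5 lets them stop at the medical record because it first offers that *or* AE review. The next sentence of 6.3.5 makes AE reporting mandatory for clinically significant worsening and for new clinically significant findings. That wording needs no change for this purpose.
- A reader might infer that the exam would give equal ascertainment under both insulins. The schedule is equal, but the examiner knows the insulin and judges clinical significance.
- A reader might take the 240 exams as a measure of lost information, or put a percentage on the reactions missed. The documents give no reaction rate and no split by source, so no such share can be supported.

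What the reply does not answer is the step from recording to analysis. Section 12 does not carry the AE record into any comparison by treatment, and the endpoint that is listed limits the source.

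**Conclusion.** The point holds as a mismatch between the endpoint's definition and the recording rules. Exam-detected infusion site reactions are collected under Sections 6.3.2.3 and 9.1.8, but as worded they lie outside the only endpoint on such reactions, and no planned AE comparison picks them up. The conclusion rests on reading the endpoint's words literally; on the looser reading the label still has to change so that the count is reproducible.

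The documents do not show that data are lost or that the comparison is biased by a known amount. The direction and size of any effect on the difference between insulins cannot be given. Importance is minor: the endpoint is secondary, the trial is exploratory, and the primary analysis is untouched.

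**What to change.** In Sections 4 and 12.4, define the endpoint as all infusion site reactions recorded under Section 9.1.8, whether the patient reported them or they were found at the scheduled exam. Tabulate them by treatment period and by source. Add two allocation rules:

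- The V8 exam is done before the switch, and its findings count to Period 1.
- A finding whose onset is unknown is assigned to the period in which it was found.

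Pointing the reference in Section 6.3.2.3 to Section 9.1.8 would be a useful tidy-up.

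The cost is a change of wording, one field for source on the reaction record and one table. The exams are already scheduled. There are two drawbacks. The second rule may misplace a few reactions that began before the switch. Both sources are open label, which is why they should be shown separately and the gain described as completeness, not as protection from bias.

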13.1 Informed Consent

In seeking and documenting Informed Consent, the Investigator must comply with applicable regulatory requirement(s) and adhere to ICH GCP and the requirements in the Declaration of Helsinki.

Before any trial-related activity, the Investigator must give the Subject verbal and written information about the trial and the procedures involved in a form that the Subject can read and understand.

The Subjects must be fully informed of their rights and responsibilities while participating in the trial as well as possible disadvantages of being treated with the trial products.

The Investigator must ensure the Subject has ample time to come to a decision whether or not to participate in the trial. A voluntary, signed, and personally dated Informed Consent must be obtained from the Subject before any trial-related activity.

The responsibility for seeking Informed Consent must remain with the Investigator, but the task may be delegated by the Investigator to a medically qualified person, in accordance with local requirements. The Informed Consent must be signed and personally dated by the person who seeks the Informed Consent before any trial-related activity.

If information becomes available that may be relevant to the Subject's willingness to continue participating in the trial, the Investigator must inform the Subject in a timely

manner, and revised Informed Consent must be provided and a new Informed Consent must be obtained.

14 Protocol compliance

Deviations from the protocol should be avoided.

Deviations should be documented and explained in at minimum in the Subject's source chart.

15 Audits and inspections

The Investigator and the site staff have an obligation to cooperate and assist in audits and inspections from domestic or foreign regulatory authorities or from IRBs/IECs. This includes giving auditors and inspectors direct access to all source documents and other documents at the trial site relevant to the clinical trial.

16 Investigator Responsibilities

All staff will conduct the trial in compliance with ICH GCP, applicable regulatory requirements and the Declaration of Helsinki.

The Investigator is accountable for the conduct of the trial. If any tasks are delegated, the Investigator shall maintain a list of appropriately qualified persons to whom he/she has delegated specified significant trial-related duties. The Investigator shall ensure that there is adequate training for all staff participating in the conduct of the trial. It is the Investigator's responsibility to supervise the conduct of the trial and to protect the rights, safety, and well-being of the Subjects.

A qualified physician, who is an Investigator or a sub-Investigator for the trial, shall be responsible for all trial-related medical decisions.

The Investigator must ensure adequate supervision of the conduct of the trial at the trial site.

17 Institutional Review Boards and regulatory authorities

Institutional Review Boards

Written approval shall be obtained from an IRB prior to commencement of the trial.

During the trial, the Investigator should promptly report the following to the IRB in accordance with local requirements: updates to IB, unexpected SAEs as applicable to IRB guidelines, protocol amendments, deviations to the protocol according to the IRB guidelines, new information that may affect adversely the safety of the Subjects or the conduct of the trial (including new benefit-risk analysis in case it will have an impact on the planned follow-up of the Subjects), annually written summaries of the trial status, and other documents as required by the local IRB.

The Investigator should maintain an accurate and complete record of all submissions made to the IRB/IEC. The records must be filed in the Investigator trial master file and copies must be sent to Novo Nordisk.

Regulatory Authorities

Regulatory authorities will receive the clinical trial application, protocol amendments, and reports on SAEs, according to national requirements.

18 Publication Plan

Public disclosure of results will be published within 4 months of completion and will include a publication of a paper in at least one scientific journal and one presentation (poster or oral presentation) at a scientific meeting.

19 References

2. Bergenstal RM, *et al*. *JAMA*. 2016;316(13):1407-1408.
3. Garg SK, *et al*. *Diabetes Technol Ther*. 2017;19(3):155-163.
4. Minimed 670G System User Guide (2016)
